8.5.8 TRIAL ENDPOINTS DEFINITION AND ASSESSMENTS

The primary endpoint will be evaluated in a non-inferiority setting, with statistical hypothesis tests formally defined in section 10.

Primary endpoint

The primary endpoint is freedom from MACCE (composite endpoint of all cause death, myocardial infarction, stroke, and valve re-intervention) at one year based on CEC adjudication.

The definitions of each component endpoint are reported in the **Table 4** below, complete definitions can be found in Appendix 4.

Table 4 Definitions of the single endpoint of MACCE

Endpoint	Definition
All cause of death	Total number of deaths regardless of cause (cardiovascular mortality + non cardiovascular mortality)
Myocardial infarction	Myocardial injury as specified in VARC-2 [1]
Stroke	Stroke is defined as an acute episode of focal or global neurological dysfunction caused by the brain, spinal cord, or retinal vascular injury as a result of hemorrhage or infarction. A stroke may be classified as “undetermined” if there is insufficient information to allow the categorization as ischemic or hemorrhagic.
Valve Re-intervention	Any re-intervention, including a transcatheter valve implant, on the implanted aortic valve bioprosthesis after surgical closure of the chest.

Secondary endpoints

1. Surgical time
 - a. Cross clamp time during index procedure
 - b. Cardiopulmonary bypass time during index procedure
2. Normalized Consumption Index and reduced Normalized Consumption Index, including resource consumption items such as (but not limited to):
 - a. Operative room time,
 - b. Duration of ICU/CCU and total hospital stay
 - c. Incidence of specific serious adverse events as defined in Appendix 3
 - d. Blood transfusion(s)
3. Quality of life questionnaire
 - a. At 1 month and 1 year post surgery
4. Intraprocedural and periprocedural serious adverse events regardless of relationship with the device within 72 hours.
5. All valve and procedure relevant serious adverse events as specified in VARC-2 guidelines [1] (Appendix 7)
 - a. Early safety at 30 days
 - b. Clinical efficacy after 30 days
 - c. Time related valve safety: SVD, endocarditis, thrombosis, thromboembolic events (excluding stroke), and bleeding annually up to 5 years
6. Serious device related adverse events up to 5 years
7. Freedom from MACCE at 2, 3, 4 and 5 years of follow up
8. Pacemaker implantation and cause up to 1 year

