It is required that a transesophageal echocardiogram (TEE) be performed to verify the performance of the valve after implantation. Intraoperative TEE is a routine part of the standard of care in management of valve patients. The results of the TEE should be recorded in the hospital patient files and dedicated eCRF.

Hospital Discharge

The hospital discharge data will be collected and entered in the eCRF preferably before the subject is discharged.

The following data listed below will be collected:

- ICU information
- Subject status
- Physical evaluation
- Modified Rankin Scale and NIHSS assessments
- Medications
- Blood sample (including WBC, RBC, hemoglobin, hematocrit, platelet count, serum LDH, haptoglobin, reticulocyte count, plasma free hemoglobin, serum creatinine, serial cardiac marker enzymes (CK-MB/Troponin) and coagulation data)

- All available platelet counts should be collected from surgery day to hospital discharge per hospital standard practice.
- Serial cardiac markers are to be collected in the perioperative (72 hour) time frame.
- 12-lead electrocardiogram (ECG)
- Echocardiographic examination (TTE) measured at investigational site (MPG; PPG, EOA, DVI, PVL)
- Serious adverse events as defined in section 17

1 month (QOL questionnaire - EQ5D)

The Quality of Life questionnaire should be completed out by the subject at 30 days \pm 7 days. This timeline is intended to ensure that the completion of QOL questionnaire will be performed by the subject himself. The information should be submitted to the site during the 1-3 months visit.

1 to 3 months Follow up visit

Follow-up evaluations are to be conducted in an office, hospital or clinic setting and are to be performed by the Principal Investigator or designee between 30 and 90 days. If the subject has been seen at another health care facility, the site is to make every effort to obtain the data required for the trial (including copies of source documents) from the subject's physician (referring or General Practitioner) in the offsite location. All efforts should be made to ensure that the subject returns to the outpatient clinic.

- Subject status (including NYHA functional classification)
- Physical evaluation
- Medications
- 12-lead electrocardiogram (ECG)
- Modified Rankin Scale and NIHSS assessments
- Blood sample (including WBC, RBC, hemoglobin, hematocrit, platelet count, serum LDH, haptoglobin, reticulocyte count, plasma free hemoglobin, serum creatinine and coagulation data)

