- Echocardiographic examination (TTE) measured at investigational site (MPG; PPG, EOA, DVI, PVL)
- Serious adverse events (as reported in section 17) including all hospitalizations

1 year FUP visit

This visit is for the evaluation of the primary endpoint and is intended to be done as a clinic visit at 1 year \pm 1 month after the day of the surgery. Follow-up evaluations are to be conducted in an office, hospital or clinic setting and are to be performed by the Principal Investigator or designee. If the subject has been seen at another health care facility, the site is to make every effort to obtain the data required for the trial (including copies of source documents) from the subject's offsite physician. All efforts should be made to ensure that the subject comes to the outpatient clinic.

The following data listed below are to be collected:

- Subject status (including NYHA functional classification)
- Physical evaluation
- Medications

- 12-lead electrocardiogram (ECG)
- Modified Rankin Scale and NIHSS assessments
- Blood sample (including WBC, RBC, hemoglobin, hematocrit, platelet count, serum LDH, haptoglobin, reticulocyte, plasma free hemoglobin, serum creatinine and coagulation data)
- Questionnaire for quality of life (recommended)
- Echocardiographic examination (TTE) measured at investigational site (MPG; PPG, EOA, DVI, PVL)
- Serious adverse events (as reported in section 17) including all hospitalizations

2 year FUP visit

This visit is intended to be done between 2 years ± 1 month after the day of the surgery. Follow-up evaluations are to be conducted in an office, hospital or clinic setting and are to be performed by the Principal Investigator or designee. If the subject has been seen at another health care facility, the site is to make every effort to obtain the data required for the trial (including copies of source documents) from the subject’s offsite physician. For this visit telephone follow up is acceptable to collect the clinical information.

The following data listed in **Table 5** below are to be collected according to the type of visit:

Table 5 Data to be collected at 2 year visit according to the type of visit.

Data to be collected	Phone call visit	Outpatient visit
Subject status (including NYHA functional classification)	X	X
Medications	X	X
Blood sample (including WBC, RBC, hemoglobin, hematocrit, platelet count, serum LDH, haptoglobin, reticulocyte, plasma free hemoglobin, serum creatinine and coagulation data)		X

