9. COMPLIANCE

Compliance will be summarized to assess adherence to protocol requirements on:

- FU visits,
- NYHA class assessment,
- Site Echocardiography,
- Core Lab Echocardiography,
- ECG and
- Blood tests.

Compliance will be defined as the number of visits/assessments actually done by a subject divided by the number of visits/assessments planned for the respective period and multiplied by 100:

$$V_i \text{ Compliance [\%]} = [\# \text{ assessments at } V_i / \text{planned } \# \text{ assessments at } V_i] \times 100.$$

An assessment will be considered as performed if a complete “assessment date” is available in the corresponding CRF.

The number of planned assessments by visits are:

- 1 to 3 months FU visit:
 - Number of patients who perform 1-3 months visit/assessment +
 - Number of patients who don't perform 1-3 months visit/assessment with >90 days FU post-implant
- 1 year FU visit:
 - Number of patients who perform 1 year visit/assessment +

- Number of patients who don't perform 1 year visit/assessment with >395 (365+30) days FU post-implant
- 2 years FU visit:
 - Number of patients who perform 2 years visit/assessment +
 - Number of patients who don't perform 2 years visit/assessment with >760 (730+30) days FU post-implant
- 3 years FU visit:
 - Number of patients who perform 3 years visit/assessment +
 - Number of patients who don't perform 3 years visit/assessment with >1125 (1096+30) days FU post-implant
- 4 years FU visit:
 - Number of patients who perform 4 years visit/assessment +
 - Number of patients who don't perform 4 years visit/assessment with >1491 (1461+30) days FU post-implant
- 5 years FU visit:
 - Number of patients who perform 5 years visit/assessment +
 - Number of patients who don't perform 5 years visit/assessment with >1856 (1826+30) days FU post-implant

At each time point, patients who complete the visit/assessment will be classified as "Completed inside window" according to the following rules:

- 1 to 3 months FU visit: if visit/assessment is performed within 30-90 days after the day of the surgery
- 1 year FU visit: if visit/assessment is performed at 365 ± 30 days after the day of the surgery
- 2 years FU visit: if visit/assessment is performed at 730 ± 30 days after the day of the surgery
- 3 years FU visit: if visit/assessment is performed at 1095 ± 30 days after the day of the surgery
- 4 years FU visit: if visit/assessment is performed at 1460 ± 30 days after the day of the surgery

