All five responses are then combined for a five-digit health state. For each five-digit health state there is a correspondent health related quality of life or score. The example in Figure 2 identifies the state '12345'.

- Each individual response to EQ-5D-5L will be converted into a single utility value by applying value sets reported in Appendix I (provided by the EuroQol website). UK coefficients will be used as primary analysis (they represent the standard). Since Germany and France will represent the top enrolling countries, the Germany-based and France-based scoring system will be used as sensitivity analyses in order to assess the robustness of results changing the country value sets. States including '9' will not be set as missing.

For example, the state '12345' would be converted in an utility value of 0.063 using the UK value set.

- The utility values will be calculated for each patient at each available time point. An averaged index value will be calculated for each time interval (i.e., Baseline – M3, M3 – Y1) as:

$$QALY_{Vi \rightarrow Vj} = k * (utility_{Vi} + utility_{Vj}) / 2$$

where $QALY_{Vi \rightarrow Vj}$ is the averaged quality of life between V_i and V_j , $utility_{Vi}$ and $utility_{Vj}$ are the utility values at visit V_i and V_j respectively, and k is a weight representing the portion of year that $V_i - V_j$ covers:

$$k = (\text{date of EQ5D at } V_j - \text{date of EQ5D at } V_i) / 365.25$$

In order to use the $utility_{Vi}$ and $utility_{Vj}$ data, the following criteria should be met:

- For M3: $(\text{date of EQ5D at M3} - \text{date of EQ5D at Baseline}) / 365.25$ is lower or equal to 0.3;
- For Y1: $(\text{date of EQ5D at Y1} - \text{date of EQ5D at Baseline}) / 365.25$ is between 0.9 and 1.1.

The quality of life between baseline to a specific time point V_i is given by the sum of all time-interval QALY from baseline to V_i . No discount rate will be applied, since evaluation is performed at 1 year.

Figure 2: Example of EQ-5D-5L form

Under each heading, please tick the ONE box that best describes your health TODAY

MOBILITY			
I have no problems in walking about			Level 1 is coded as a '1'
I have slight problems in walking about			
I have moderate problems in walking about			

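### The SAP's QALY counts its acceptance limits from the baseline questionnaire, so late but in-window forms can be unusable after a long pre-operative gap, and it has no 1-month node.

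*SAP*

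**What the plan says.** SAP 12.3 builds the QALY by a trapezoidal rule. The intervals are given as "i.e., Baseline – M3, M3 – Y1". Each is weighted by the days between the two questionnaire dates divided by 365.25, and the intervals are summed from baseline. For a utility to be used, "the following criteria should be met": the time in years from the baseline EQ-5D to the M3 form "is lower or equal to 0.3", and to the Y1 form it "is between 0.9 and 1.1".

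The visit windows start elsewhere. SAP 9 classes a visit as inside its window by days from the operation: "1 to 3 months FU visit: if visit/assessment is performed within 30-90 days after the day of the surgery", and 365 ± 30 days for the one-year visit. SAP 5.4 and Protocol 8.7.1 also count from surgery. SAP 5.4 takes baseline as the last assessment before the operation. Protocol 8.7.1 places the baseline EQ-5D after consent. Neither document limits the time from that form to surgery.

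On which forms exist, the quality-of-life endpoint in Protocol 8.5.8 is set "At 1 month and 1 year post surgery". For the 1-month form, Protocol 8.7.1 says "The Quality of Life questionnaire should be completed out by the subject at 30 days", with a tolerance of 7 days, and SAP 5.4 labels this assessment M1. The flow chart (Protocol 4.2) marks the EQ-5D at 1 month, at 1-3 months and at 1 year. The 1-3 month list in 8.7.1 contains no EQ-5D; the 1-month form is only handed in at that visit. The one-year list carries it with a qualifier: "Questionnaire for quality of life (recommended".

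**The concern.** Two clocks are in use. A patient can attend on time by SAP 9 and still have a form that SAP 12.3 will not use, because days spent waiting between the baseline form and surgery count against the limit. The M3 form ends the first QALY interval and starts the second, so losing it removes both.

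The choice of nodes is a separate matter. The plan draws a straight line from baseline to M3 although a 1-month measurement lies between them. That stretch covers early recovery, where the protocol's health-economics section (6.3) expects a benefit from the shorter operation. A site that follows the 8.7.1 list rather than the flow chart would collect no M3 form, and then neither stated interval can be computed.

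At stake are the completeness of the QALY and its ability to reflect the first weeks after surgery.

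**Working it through.** **Inputs.** Acceptance limits of 0.3, 0.9 and 1.1 years from the baseline form, and the weight formula (SAP 12.3); 365.25 days per year (SAP 12.3 and 18.7); visit windows of days 30-90 and 335-395 after surgery (SAP 9). The gap g, in days from baseline form to surgery, is not in the documents and is varied. Visits are assumed to spread evenly over each 60-day window.

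**Step 1: limits in days after the baseline form.**
- M3: 0.3 × 365.25 = 109.6, with no lower limit.
- Y1: 0.9 × 365.25 = 328.7 to 1.1 × 365.25 = 401.8.

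**Step 2: room before an in-window form is lost.** A form d days after surgery lies d + g days after the baseline form.
- Y1 on day 395: 401.8 − 395 = 6.8 days.
- Y1 on day 365: 401.8 − 365 = 36.8 days.
- M3 on day 90: 109.6 − 90 = 19.6 days.
- Early Y1 forms are never lost: day 335 is already above 328.7 with g = 0.

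**Step 3: share of in-window forms dropped.** Y1: (395 + g − 401.8)/60. M3: (90 + g − 109.6)/60. Negative values are set to zero.

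| Assumed gap g (days) | Y1 dropped | M3 dropped |
|---|---|---|
| 0 to 6 | 0% | 0% |
| 14 | 7.2/60 = 12% | 0% |
| 30 | 23.2/60 = 39% | 10.4/60 = 17% |
| 45 | 38.2/60 = 64% | 25.4/60 = 42% |
| 60 | 53.2/60 = 89% | 40.4/60 = 67% |

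**Step 4: the same limits counted from surgery.** Day 90 is 0.246 year, and days 335 to 395 are 0.917 to 1.081 years. All fall inside the limits, so no in-window form would be lost.

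**Step 5: effect of leaving out M1.** If the 1-month utility lies δ below the straight line from baseline to M3, the omitted area is a triangle, and the plan's QALY is too high by δ × (days from baseline form to M3)/2/365.25. For δ = 0.10:
- M3 on day 45, g = 0: 0.10 × 45/2/365.25 = 0.006.
- M3 on day 90, g = 0: 0.10 × 90/2/365.25 = 0.012.
- M3 on day 90, g = 30: 0.10 × 120/2/365.25 = 0.016.

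For assumed δ from 0.05 to 0.20, M3 from day 45 to 90 and g from 0 to 30, the range is 0.003 to 0.033 per patient. The effect on the difference between arms depends on how the arms differ at 1 month, which the documents do not give.

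**The case against.** The best defence is that the baseline anchor has a purpose. The weights run between questionnaire dates and the sum starts at the baseline form, so a limit of 0.9 to 1.1 years from that form keeps the accumulated time near one year. This stands, and it rules out simply moving the windows. If only the limits moved to surgery, a day-395 visit after a 60-day gap would accumulate 455 days (1.25 years), against 335 days (0.92 year) for a day-335 visit with no gap. The QALY would then partly measure waiting time.

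It is also fair that nothing formal rests on the QALY. It is derived in the SAP and summarised descriptively. The endpoint in Protocol 8.5.8 is the questionnaire, not the QALY.

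A reader might infer three stronger things that the documents do not support:
- *Any pre-operative wait loses valid forms.* It does not. Gaps of up to 6 days lose nothing, and only forms late in their window are at risk. The documents neither state nor bound the gap, so no actual loss can be read from them.
- *Early recovery is not measured.* The 1-month form is collected. SAP 12.3 summarises index and VAS values at each follow-up assessment, fits a repeated-measures model with a treatment-by-time term, and adds Mann-Whitney tests. None of these is stated to use the QALY limits or to exclude M1.
- *The plan has no 1-3 month EQ-5D.* The flow chart is part of the protocol and schedules one. The fault is that the text and the flow chart disagree.

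**Conclusion.** The point holds, confined to the QALY. The acceptance limits and the visit windows have different origins and the gap between those origins is uncapped, so late in-window forms can be unusable. The thresholds of about 7 days (Y1) and 20 days (M3) follow from the plan's own figures. The percentages dropped also rest on the assumed gaps and uniform visit timing; they show sensitivity and do not predict the loss.

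The missing 1-month node and the disagreements between Protocol 4.2 and 8.7.1 need no assumption. The node's effect is modest per patient, and its direction in the comparison of arms is unknown. This is a low-severity correction that leaves the primary analysis and the formal quality-of-life comparisons untouched.

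**What to change.** In SAP 12.3:
- Accept M3 and Y1 forms by the surgery-anchored visit windows already used in SAP 9.
- Start the integral at surgery, assigning the last preoperative utility to the surgery date, and standardise the result to one year so that neither waiting time nor visit timing enters it.
- Use the nodes Baseline, M1, M3 and Y1, and state a rule for a missing M3 form.

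In the protocol:
- Reconcile 8.7.1 with the flow chart on whether an EQ-5D is collected at 1-3 months.
- Reconcile the recommended status of the one-year EQ-5D in 8.7.1 with its unqualified entry in the flow chart and its standing as a named secondary endpoint.

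The cost is SAP derivation wording and minor protocol text corrections. The M1 and Y1 forms, and the M3 form in the flow chart, are already scheduled, so no new data collection is needed beyond settling the M3 question.

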12.3. HEALTH STATUS (EQ-5D-5L)

The number and proportion of subjects of each level (1 - no problems, 2 - slight problems, 3 - moderate problems, 4 - severe problems, 5 - extreme problems) for each dimension (mobility, self-care, usual activities, pain/discomfort, and anxiety/depression) will be reported. The change in numbers and proportions from baseline to post-implant FU will be calculated⁹. The tables will be shown by treatment arm.

The Paretian classification⁹ will be applied at each available post-implant FU according to the following rules:

- A health profile is better than another if it is better in at least one dimension, and is no worse in any other dimension.
- A health profile is worse than another if it is worse in at least one dimension, and is no better in any other dimension.

Using this principle to compare a patient's EQ-5D health states between any two time periods, there are only 4 possibilities:

1. Their health state is better
2. Their health state is worse
3. Their health state is exactly the same
4. The changes in health are 'mixed': better on one dimension, but worse on another.

According to the above classification, changes from baseline in health status by treatment arm will be reported. Additionally, changes from baseline will be displayed as pie charts (by treatment and by each available post-implant assessment).

EQ-5D-5L answers to each dimension (health states) will be converted into a single index value. The index values allow the calculation of quality-adjusted life years (QALYs) that are used to inform economic evaluations of health care interventions. The idea underlying the QALY is that a year of life lived in perfect health is worth 1 QALY (1 Year of Life × 1 Utility = 1 QALY) and that a year of life lived in a state of less than this perfect health is worth less than 1. In order to determine the exact QALY value, it is requested to multiply the index value associated with a given state of health by the years lived in that state. The steps to obtain a QALY are:

1. Each dimension of the EQ-5D-5L questionnaire will be scored as follow:
 - Level 1 will be coded as '1'
 - Level 2 will be coded as '2'
 - Level 3 will be coded as '3'
 - Level 4 will be coded as '4'
 - Level 5 will be coded as '5'
 - Missing or ambiguous values (e.g. 2 boxes are ticked for a single dimension) will be coded as 'g'.

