18.5. HANDLING OF MISSING VALUES

At each time point/visit, all subjects still in the study are reported. Missing values will be taken into account as missing in the analysis. The number of observed values and the number of missing values must sum up to the number of subjects in the study at the respective time point/visit.

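### The 1-year QALY in SAP 12.3 has no term for death, so the by-arm summary covers only living patients with in-window questionnaires and does not reflect mortality

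*SAP*

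**What the plan says.** SAP 12.3 explains that to obtain a QALY "it is requested to multiply the index value associated with a given state of health by the years lived in that state". It then sets out the calculation:

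- "The utility values will be calculated for each patient at each available time point".
- "An averaged index value will be calculated for each time interval" (Baseline–M3 and M3–Y1) as k × (utility at Vi + utility at Vj) / 2, where the two terms "are the utility values at visit V_i and V_j respectively" and k is the time between the two EQ-5D dates divided by 365.25.
- The M3 utility is usable only if its questionnaire falls at most 0.3 years after the baseline one. The Y1 utility is usable only if that interval "is between 0.9 and 1.1".
- For the cumulative QALY, "The quality of life between baseline to a specific time point" "is given by the sum of all time-interval QALY from baseline to V_i".

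The QALY and the index are then summarised descriptively as changes from baseline at each follow-up. SAP 5.1 makes all tables by treatment group. The MMRM is on the EQ-5D index, and the Mann-Whitney tests are on the index and EQ VAS.

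The general missing-data rule in SAP 18.5 reads: "At each time point/visit, all subjects still in the study are reported. Missing values will be taken into account as missing in the analysis". Table 4 in SAP 6.6 assigns the cost-effectiveness analyses, which include 12.3, to the Safety and mITT populations.

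**The concern.** A QALY combines length and quality of life, so a year not lived counts as zero. The formula in SAP 12.3 cannot produce that zero. A patient who has died has no later questionnaire, hence neither a closing utility nor a closing date, and the interval is undefined. The patients with the largest loss are the ones left out of the 1-year figure. All-cause death is part of this trial's primary endpoint, and the SAP says the index values serve to inform economic evaluation. Side-by-side arm means labelled as QALYs will be read as including mortality when they do not.

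**Working it through.** **Is there a rule for death elsewhere?** None was found. Multiple imputation is specified for haemodynamics and leaks (SAP 11.2) and for the consumption indexes when 5% or more are missing (SAP 12.2.2), but not for EQ-5D or QALY. Protocol 10.8 leaves missing-data methods to the SAP. The statement in 12.3 about states containing a 9 concerns unanswered items on a returned form.

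**What the formula gives.**

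| Patient | Baseline–M3 | M3–Y1 | 1-year QALY |
|---|---|---|---|
| Alive, both questionnaires in window | defined | defined | defined |
| Dies before M3 | undefined | undefined | none |
| Dies between M3 and Y1 | defined | undefined | missing, or first interval only |
| Alive, Y1 missing or out of window | defined | undefined | missing, or first interval only |

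**Size.** The documents give no QALY figure to reproduce and no utilities. The utilities and times of death below are assumptions.

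Inputs:
- Utilities at baseline, M3 and Y1: 0.75, 0.82, 0.85 (assumed; range 0.70/0.75/0.80 to 0.80/0.88/0.90).
- M3 at day 60, Y1 at day 365 (assumed).
- Half of deaths at day 15 and half at day 200 (assumed), with utility falling linearly to 0 at death.
- One-year mortality from 4.5% (cardiac deaths only, the CAVALIER trial, Protocol 6.2) to 9.5% (one-year survival 90.5%, the 314-patient European multicentre series, Protocol 6.2). This is about 28 to 59 deaths in an arm of 617. The blinded pooled MACCE-free rate of 91% (SAP 2.3) implies pooled mortality of at most about 9%, since death is a component, so 9.5% is a ceiling.

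Per-patient values:
- Survivor: (60/365.25) × (0.75 + 0.82)/2 + (305/365.25) × (0.82 + 0.85)/2 = 0.129 + 0.697 = 0.826. Over the utility range and M3 at day 60 or 90, this is 0.762 to 0.881.
- Death at day 15: (15/365.25) × 0.75/2 = 0.015.
- Death at day 200: 0.129 + (140/365.25) × 0.82/2 = 0.286.
- Mean for a death: (0.015 + 0.286)/2 = 0.151. Mean loss per death: 0.826 − 0.151 = 0.675.

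Overstatement of an arm mean = mortality × 0.675:

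| Mortality | Mean with deaths counted | SAP rule | Overstatement |
|---|---|---|---|
| 4.5% | 0.796 | 0.826 | 0.030 |
| 7.0% | 0.779 | 0.826 | 0.047 |
| 9.5% | 0.762 | 0.826 | 0.064 |

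Between arms, with identical survivors, the SAP rule shows a difference of 0.000. Counting deaths gives −0.017 at 7.0% versus 4.5% mortality and −0.034 at 9.5% versus 4.5%.

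Two checks on the assumptions:
- A simpler set (0.85 for a survivor, 0.21 for a death, loss 0.64) gives 0.026, 0.038 and 0.051 at 4%, 6% and 8% mortality, and 0.03 × 0.64 = 0.019 for a 3-point difference.
- Holding the last utility flat until death gives 0.031 and 0.443 for the two deaths, a mean loss of 0.589, and an overstatement of 0.027 to 0.056 at 4.5% to 9.5%.

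**If available intervals are added instead.** The day-200 death keeps 0.129, and so does a living patient with no usable Y1 form, whose value would be about 0.826. Over the utility range and M3 at day 60 or 90, the truncated value is 0.119 to 0.207. The day-15 death still has no value.

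**The case against.** Several points on the other side stand.

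- **No test rests on QALY.** It is a descriptive table, and Protocol 8.5.8 lists only the questionnaire at 1 month and 1 year as an endpoint. A reader might infer that a formal treatment comparison is biased. The documents plan none on QALY.
- **The sum is not defined when an interval is missing.** Section 12.3 could be read as adding what is available, which would penalise a death after M3 heavily. SAP 18.5 points towards leaving the value missing, but it is a general display rule. On either reading, deaths before M3 have no value and later deaths are not distinguished from non-response. A patient who dies after completing M3 does count in the M3 summary.
- **Survivors only is not quite the set.** Living patients with a missing or out-of-window form also drop out, and Protocol 8.7.1 makes the 1-year questionnaire only recommended.
- **The arms may match.** Protocol 10.2 expects similar freedom from MACCE. If mortality and its timing are alike, the overstatement largely cancels between arms.
- **Deaths are visible elsewhere.** They are in the primary endpoint, its component analysis, the time-to-event analyses and the adverse event tables. SAP 5.2 also shows the number of non-missing observations.

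A reader might also infer that the valve with more deaths would look better because frailer patients leave its average. That is not shown. The calculation uses one survivor value for both arms, so it demonstrates a hidden difference, not a reversed one.

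**Conclusion.** The point holds for the descriptive 1-year QALY. Followed as written, SAP 12.3 leaves patients who die out of that figure or gives those who die after M3 a value that does not represent their death. This conflicts with the SAP's own definition of a QALY and with the Safety and mITT sets named for the section, both of which include patients who die. Under the assumed utilities and times of death, and 4% to 9.5% one-year mortality, an arm mean is too high by about 0.03 to 0.06 QALY. A between-arm distortion of about 0.02 QALY needs an assumed mortality difference of 2.5 to 3 points, which the documents do not predict. The primary analysis and the EQ-5D index and EQ VAS tests are unaffected.

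**What to change.** Add to SAP 12.3: *For patients who die, utility is 0 from the date of death; the last interval runs from the last available questionnaire to the date of death, with utility 0 at its end, and QALYs after death are 0.*

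This rule alone is not enough. If deaths are scored while living non-responders are dropped, deaths are over-weighted: with mortality m and a response fraction r among the living, their weight becomes m / (m + (1 − m) r), which exceeds m whenever r is below 1. So also state that, for living mITT patients with a missing or out-of-window questionnaire, the utility is imputed, for example by multiple imputation under missing at random as in SAP 11.2 and 12.2. Then report 1-year QALYs by arm in the mITT population.

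The cost is one derivation rule and one imputation model in a SAP amendment. Date of death is already collected and derived in SAP 18.12. No new data or visits are needed, and the primary analysis does not change.
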